3.4 Clinical Evidence to Date

RhC1INH has not been assessed in patients with COVID-19 or related CoV infections in a clinical trial setting. RhC1INH has been extensively investigated in the treatment of acute attacks in patients with hereditary angioedema having demonstrated efficacy and safety (please, see IB for further details). In addition, a recent randomized, double-blind, placebo-controlled pilot study has demonstrated its efficacy and safety regarding attenuation of acute renal injury in patients undergoing elective coronary angiography⁴².

With regards to infection and inflammation, pdC1INH treatment reduced the collateral damage caused by hyperinflammation in human sepsis in several small pilot studies³⁵⁻³⁷. In particular, it decreased complement and neutrophil activation⁴³. Also, a reduced occurrence of capillary leakage after allogeneic stem cell transplantation has been observed in a further study in line with a decrease in the complement C5 activation product C5a^{38, 44}.

We have recently treated five patients admitted with stage II COVID-19 infection with compassionate use rhC1INH in addition to SOC in order to limit pulmonary inflammation and subsequent deterioration. RhC1INH was administered every twelve hours over 48 hours starting with a loading dose of 8400 U and continuing with 4200 U. RhC1INH was well tolerated with no treatment-emergent adverse events. Three patients had an immediate favorable response with rapid defervescence and decline in inflammatory markers and were discharged within a week. Two patients were administered additional treatment with tocilizumab and recovered afterwards, although one of these two patients rapidly progressed after 24 hours of treatment requiring transient mechanical ventilation.

3.5 Dose Rationale / Medical Device: Rationale for the Intended Purpose in Study (pre-market MD)

Pharmacological Characteristics

A phase 1, dose-escalating study in 12 asymptomatic patients with HAE demonstrated that rhC1INH administration provides a dose-dependent restoration of complement homeostasis. Patients with functional C1-INH levels <40% and C4 levels <300 µg/mL (values expectable in patients with HAE) received 2 IV doses of rhC1INH (range 6.25 to 100 U/kg), with a washout period of ≥5 weeks. A dose-dependent, biologic activity was demonstrated by increased plasmatic levels of C4, which is a substrate for activated C1s: 12 hours after rhC1INH administration (100 U/kg), the mean plasma levels of C4 were approximately double compared to baseline. Comparable results were shown after the 50 U/kg dose of rhC1INH, which was associated with a maximum C4 level of approximately 1.76-fold that at baseline, achieved after 10.7 hours.

A pharmacokinetic modelling indicated that a single IV injection of rhC1INH at a dose of 50 U/kg restores functional C1-INH levels to at least the lower limit of the normal range in almost all patients⁴⁵.

Following the slow IV administration (15 min) of 50 U/kg of rhC1INH to 6 asymptomatic patients with HAE, the mean maximum plasmatic level of functional C1-INH was 1.36 U/mL, mean volume of distribution was similar to plasma volume (approximately 3 L), mean elimination half-life was 2.4 hours and clearance was approximately 23 mL/min⁴⁶.

The pharmacokinetic data derived from the phase 1 studies demonstrated that the half-life of rhC1INH is shorter than plasma-derived C1-INH which is due to the different glycosylation of rhC1INH, leading to more rapid hepatic clearance compared to plasma-derived C1-INH.

In a phase 1 study in healthy volunteers, patients were administered rhC1INH on 5 occasions with intervals of at least 3 weeks. 14 patients received a total of 59 administrations of rhC1INH at a dosage of 100 U/kg. The mean elimination half-life was 2.7 hours and the baseline corrected Cmax was 2.6 U/mL. These values were comparable to those estimated in other studies. The course of functional C1-INH levels after infusion of 100 U/kg of rhC1INH was identical after 1st, 3rd and 5th administration.

RhC1INH is cleared via mannose/asiagalactosidase receptors on macrophages and hepatic cells with carbohydrate recognition. RhC1INH is not expected to be excreted, but to be fully eliminated by degradation. As there are no clinical data with rhC1INH in patients with hepatic impairment, and as hepatic impairment may prolong the plasma half-life of rhC1INH, patients with chronic liver disease will be excluded from study participation.

Safety

The clinical safety data analysis demonstrated that rhC1INH at doses of 50 and 100 U/kg are generally safe and well tolerated when administered for treatment of acute attacks in patients with HAE⁴⁷. The adverse event profile found in the randomized, placebo-controlled studies was similar for patients treated in the rhC1INH and saline treatment groups.

Throughout the clinical development, no safety signal related to hematology, biochemistry, coagulation, urinalysis, vital signs, or ECG parameters was noted. Evidence regarding a thrombogenic risk of rhC1INH has not been recorded during clinical development and clinical studies. RhC1INH had no effect on activation of coagulation and fibrinolysis⁴⁸.

Because rhC1INH is derived from the milk of transgenic rabbits and contains a small percentage (0.002%) of Host-Related Impurities (HRI), immunogenicity was extensively tested

throughout the clinical development programs, leading to the evidence that rhC1INH has low potential to induce anti-C1-INH antibodies or anti-HRI response. The use of the product in patients allergic or suspected to be allergic to rabbits should be avoided because of the risk of an allergic reaction.

Sporadic, transient immune responses to rhC1INH and HRI were observed, but with no associated clinical findings. No patient developed neutralizing antibodies to C1-INH. No impact of immunogenicity on clinical efficacy or safety was observed.

There was no plausible temporal association between treatment-emergent adverse events or new acute attacks and the presence of any confirmed anti-C1-INH or anti-HRI antibodies in patients with HAE.

No patients tested positive for neutralizing antibodies to endogenous C1-INH or rhC1INH and no induced anti-rabbit IgE antibodies were reported. Healthy patients with clinically manifest rabbit allergy were administered rhC1INH by skin prick and – in case of lack of allergic response – an intradermal and subcutaneous injection. Two out of twenty patients revealed a positive response, suggesting that even in patients with a pre-existing allergy to rabbits the risk of a hypersensitivity reaction upon administration of rhC1INH is limited.

Lastly, safety was favorable with no related or treatment-emergent adverse events in a recent double-blind, placebo-controlled trial in elderly patients undergoing elective coronary angiography⁴².

Description and Justification of Route of Administration and Dosage

Because C1-INH is a plasma glycoprotein, an IV route of administration has been chosen for the existing indication (acute attacks in patients with HAE). The same route of administration will be used in this study.

The approved dose for treatment of acute attacks in patients with HAE is 50 U/kg (up to 4200 U), with an option to repeat the dose once based on clinical symptoms. Studies on prophylactic usage at a dose of 50 U/kg (up to 4200 U) twice weekly, up to 4 weeks, to treat patients with HAE with frequent acute attacks appeared efficacious and well tolerated. Maximum doses (4200 U or 8400 U) have been administered to patients weighing 84 kg or more.

In the current study, rhC1INH (150 U/ml) at a 50 U/kg dose (max dose of 4200 U) will be administered as a slow IV injection over a period in approximately 5 minutes every 12-hours for 4 days. The dosage regimen was chosen based on the following rationale

- Although C1INH antigenic concentrations are often elevated in patients with infections (C1INH is an acute phase reactant), the functional activity may be compromised as a consequence of modified/cleaved and consequently inactive C1INH⁴⁹.
- The half-life of rhC1INH is 2.5 hours, hence in order to achieve a sustained inhibition of the CS and KK system, repeated administration has been chosen. Despite the short half-life sustained inhibition of the target proteases may be guaranteed related to the irreversible inhibition of target proteases followed by clearance from the bloodstream. In order to balance effectiveness with practicability and potential toxicity we decided to limit the total daily dose and administer rhC1INH every 12 hours.
- Repeated administration of rhC1INH over four days has been chosen, as hyperinflammation may develop several days after the admission, in particularly during the time of seroconversion (development of antibodies against SARS-CoV-2)⁵⁰. Anti-inflammatory strategies, such as the current proposed treatment regimen with rhC1INH may have a particular role at the time of induction of hyperinflammation. Hence, treatment for at least 4 days is warranted.

Participants will either receive rhC1INH with SOC or only SOC.

3.6 Explanation for Choice of Comparator

Currently, no approved or effective treatment options for COVID-19 infections exist. Participants will either receive rhC1INH plus SOC or only SOC. SOC may include treatment for underlying comorbidities and management of COVID-19 symptoms. Importantly, local treatment protocols including drugs with perceived benefits in COVID-19 infections such as lopinavir/ritonavir are allowed as long as they are declared as SOC. In order to facilitate patient recruitment in a time of restricted human and financial resources, and because of an objective primary endpoint, a placebo group will be omitted.

Diphenhydramine, hydroxychloroquine, and azithromycin are associated with prolongation of the cardiac QT interval, and subsequent increased risk of fatal cardiac arrhythmia.

Cardiovascular monitoring will be conducted in severely-ill subjects receiving multiple drugs on a case-by-case adjudication of any prolongation of QT intervals to evaluate the benefit-risk of continued participation in the clinical study.

3.7 Risks / Benefits

Despite strong reasons for a benefit of rhC1INH in the setting of hyperinflammation, it is unclear if participants in the current study will receive any immediate benefit from treatment with rhC1INH. However, the knowledge gained from this study may help to better understand the pathophysiology of ALI and hyperinflammation in SARS-CoV-2 and related CoV infections. In addition, this trial may serve as pilot study for future rhC1INH studies in patients with severe infections characterized by hyperinflammation and subsequent tissue damage.

Previous experimental models have not suggested a detrimental effect of complement inhibition on viral replication, and C1-INH treatment has not been associated with an increased risk for secondary bacterial or viral infections in humans.

RhC1INH is approved for the treatment of acute angioedema attacks in adult and adolescent patients with HAE in the EEA countries and the United States and for adults in South Korea and Israel. Up to October 2019, 268 unique patients have been exposed to rhC1INH in the rhC1INH clinical development program and 3717 patients worldwide have been commercially prescribed rhC1INH without any change to the risk-benefit profile.

To date, the only known relevant clinical risk associated with rhC1INH is the possibility of an allergic reaction to Host-Related Impurities (rabbit). Patients with medical history of allergy to rabbits or rabbit-derived products including rhC1INH or suspicion of such an allergy, are excluded from participation.

To minimize the risk for allergic reactions to rhC1INH, treated patients will be monitored for clinical symptoms of hypersensitivity during and after dosing. All treatments will be administered in a hospital and all patients will stay under close observation until discharge from the hospital.

RhC1INH was demonstrated to be a safe option for reducing the risk of contrast-induced renal damage in high-risk patients⁴². In addition, rhC1INH was safely administered to five patients suffering from stage II COVID-19 infection.

Expected Adverse Events During the Study

As per last the Investigator's Brochure, expected adverse reactions are described as follows: The clinical development program supporting safety of rhC1INH is based on a total number of 268 unique patients (up to Oct 2019). Those 268 patients received a combined total of almost 1600 administrations of rhC1INH. The treatment emergent adverse events (TEAEs) that occurred with onset within 7 days of treatment with rhC1INH that were most frequently reported (observed in $\geq 3\%$ of patients treated with rhC1INH) were headache (11%), nausea, and

diarrhea (3% each). There was no evidence of an increase in the percentages of patients with TEAEs or related TEAEs, or in the seriousness or severity of TEAEs, with increases in rhC1INH dose, treatment of a larger number of attacks, and/or treatment of a single attack with an additional dose.

As described in the US prescribing information for rhC1INH, AEs of headache, sneezing, angioedema, erythema marginatum, skin burning sensation, back pain, C-reactive protein increased, fibrin D-dimer increased, vertigo, lipoma, nausea, and diarrhea occurred in $\geq 2\%$ of rhC1INH -treated patients. Note that AEs are listed in the US prescribing information regardless a causal relationship with rhC1INH. The frequency of adverse reactions listed above is defined using the following convention:

- Very common ($\geq 1/10$),
- Common ($\geq 1/100$ to $< 1/10$),
- Uncommon ($\geq 1/1,000$ to $< 1/100$),
- Rare ($\geq 1/10,000$ to $< 1/1,000$),
- Very rare ($< 1/10,000$),

Specific antidotes against rhC1INH do not exist. In the unlikely event of an allergic reaction, standard treatment regimens indicated by the clinical situation (e.g. epinephrine, antihistamines, corticosteroids, etc.) will be administered.

The level of risk may evolve over time, during the study: consequently, a Data Safety Monitoring Board (DSMB) will monitor the safety of all patients, as well as the continuing validity and scientific merit of the study.

3.8 Justification of Choice of Study Population

Approximately 20% of patients with COVID-19 infection require hospitalization for supportive treatment. The majority of these patients will suffer from viral pneumonia visible on chest CT scans or Chest X-Ray. Approximately 15-20% of these patients will progress to severe ALI requiring mechanical ventilation and ICU support. Patients with confirmed COVID-19 disease (based on a positive SARS-CoV-2 PCR result) and admitted to a non-ICU ward will be eligible for the study. This population was chosen, as anti-inflammatory treatments such as rhC1INH may interfere most effectively during stage II disease, *i.e.* during the early inflammatory response phase. In addition, interventions that prevent patients from deteriorating and requiring mechanical ventilation are highly desired and represent an area of unmet clinical need in a pandemic situation with limited ICU and ventilation support capacity. This population offers the opportunity to impact not only on an individual but also on a population level.

4. STUDY OBJECTIVES

4.1 Overall Objective

The purpose of this study is to determine whether rhC1INH administered early during hospital admission for COVID-19 provides additional benefit compared to SOC alone with regards to the clinical course of patients by limiting the local and systemic inflammatory response, and to describe its safety profile in this population.

4.2 Primary Objective

The primary objective of the study is to determine if adding 4 days of treatment with rhC1INH to SOC treatment in adult participants admitted with non-critical COVID-19 infection will affect disease severity including progression to severe disease requiring mechanical ventilation within 7 days after enrollment as assessed by the WHO Ordinal Scale for Clinical Improvement.

4.3 Secondary Objectives

To evaluate the effect of rhC1INH treatment in addition to SOC treatment compared to only SOC treatment on disease progression as measured by

- Time to clinical improvement (time from randomization to an improvement of two points on the seven-category WHO ordinal scale or live discharge from hospital, whichever came first) within 14 days after enrollment.
- Proportion of participants alive and not having required invasive or non-invasive ventilation at 14 days after enrollment.
- Proportion of subjects with ARDS (defined by Berlin severity criteria) within 14 days after enrollment

4.4 Safety Objectives

The study aims to assess the safety of rhC1INH treatment in patients admitted with COVID-19 infection and receiving SOC treatment including overall incidence of adverse and serious adverse events and their relationship to the study treatment during a 3 month follow-up period.

5. STUDY OUTCOMES

5.1 Primary Outcome

The primary endpoint will be the disease severity on the 7-point WHO Ordinal Scale on Day 7. This endpoint has been suggested by WHO for clinical trials in patients with COVID-19. The ordinal scale measures illness severity over time.

Figure 2: WHO ordinal scale for clinical improvement.

Patient State	Description	Score
Outpatient	No limitation in activities	1
	Limitation in activities	2
Hospitalized Mild disease	No oxygen therapy	3
	Oxygen by mask or nasal prongs	4
Hospitalized Severe disease	Non-invasive ventilation or high-flow oxygen	5
	Intubation, mechanical ventilation +/- additional organ support	6
Death	Death	7

5.2 Secondary Outcomes

The secondary endpoints will evaluate the effect of rhC1INH treatment in addition to SOC treatment relative to only SOC treatment on disease progression as measured by

- Time to clinical improvement (time from randomization to an improvement of two points on the seven-category WHO Ordinal Scale or live discharge from hospital, whichever came first) within 14 days after enrollment.
- Proportion of participants alive and not having required invasive or non-invasive ventilation at 14 days after enrollment.
- Number of days hospitalized (per patient)
- Number of days alive (per patient)

- Proportion of subjects with ARDS (defined by Berlin severity criteria) within 14 days after enrollment

5.3 Other Outcomes of Interest

- Changes on the WHO Ordinal Scale from baseline over 14 days
- Length of hospital stay until day 28 in survivors.
- Proportion of participants progressing to mechanical ventilation on day 7 and day 14
- Proportion of participants requiring ICU treatment on day 7 and 14
- Length of ICU stay until day 28
- Ventilator-free days until day 28
- All-cause mortality (time from randomization to death within 4 weeks)
- Changes in biomarker levels until day 14: CRP, LDH, D-dimer, ferritin, IL-6, lymphocyte count
- Time to virological clearance of SARS-CoV-2 by PCR from upper or lower respiratory tract samples (time from enrollment to first of 2 negative assays at least 12 hours apart)
- Proportion of patients receiving additional anti-inflammatory treatment such as tocilizumab or immunoglobulins within 14 days
- Time to defervescence (temperature $<38.0^{\circ}\text{C}$ sustained for at least 48 hours)
- Time to clinical improvement (defervescence, normalization of oxygen saturation ($>93\%$) and respiratory rate) until day 28
- Duration of supplemental oxygen until day 28
- In a subgroup of patients, the pharmacokinetics and pharmacodynamics of rhC1INH in COVID-19 patients will be characterized by measuring the concentration of rhC1INH and the activity of C1-INH and proteins (such as C3, C4).

5.4 Safety Outcomes

The study will evaluate the safety of rhC1INH in the setting of COVID-19 infections if added to SOC compared to SOC treatment only by measuring the incidence of adverse events up to 3 months post-treatment.

6. STUDY DESIGN

6.1 General Study Design and Justification of Design

This is an exploratory, randomized, parallel-group, open-label, multi-center, phase 2 clinical study in patients with confirmed COVID-19 infection and admitted to the hospital for treatment of SARS-CoV-2 infection to estimate the effect size of rhC1INH treatment compared to SOC on the proportion of patients surviving without requiring mechanical ventilation.

The study will recruit approximately 120 patients (80 patients in the intervention and 40 in the control arm) from approximately five to ten sites in the United States. Sites will be selected on the basis of estimated numbers of cases, the availability of a committed principal site Investigator and research team, and the capacity to collect samples as per protocol.

Participants will be randomly assigned in a 2:1 ratio to rhC1INH treatment in addition to standard of care (SOC) or SOC stratified by the site. Screening, informed consent and randomization will happen as early as possible after admission to the hospital, usually within 48 hours after admission. Participants will receive intravenous rhC1INH in addition to standard of care (SOC) or SOC during an admission period starting on the day after informed consent (=day 0). Both groups will continue to receive SOC treatment for COVID-19 infection. Blood samples will be collected before and during the 4-day period of treatment. Follow-up will include the period until discharge and a weekly telemedicine interview or telephone call for 3 months post treatment to assess potential adverse events and outcomes.

Duration of participant's participation will be approximately 14 weeks (+/- 5 days). Screening phase duration is up to 48 hours; intervention period is 14 days (including a treatment phase of 4 days) and follow-up period of 3 months starting post-treatment on Day 0. After discharge, follow-up information is obtained on a weekly basis until 3 months post-treatment. When no response is received within 5 weeks following discharge the participant may be considered as lost to follow-up.

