9.1.4 Assessment of Safety Outcomes

9.1.4.1 Adverse events

Participants will be followed for adverse events and outcomes for 3 months post treatment (Day 0). Assessments will be done daily while in the hospital and via a weekly follow-up telemedicine interview or telephone call after discharge.

Adverse events and clinical course including death within 4 weeks will be assessed by a weekly telemedicine or structured telephone interview for 3 months post-treatment. If necessary, medical charts will be reviewed, discharge summaries will be reviewed, or the patients' general practitioner will be contacted regarding specific follow-up information.

Every effort will be made to contact the trial subject and obtain complete data for follow-up. Conditions that started before signing informed consent will be recorded as medical history. Conditions that started or deteriorated after signing informed consent will be documented as AE. Definition of AE and SAE will be found in Section 10.

All AEs will be assessed and documented by the Investigators according to seriousness, intensity, causal relationship with study treatment, action taken with study treatment (e.g. withdrawal), specific treatment for AE and outcome. In addition, time of onset and AE duration will be recorded. Procedures are defined in Section 10. AEs will be recorded on the respective CRF pages. Participants will be asked about any new events/complaints during the hospitalization and up to 3 months post treatment. In addition, participants are asked to report any new events including hospital admission to the study team.

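### Section 6.1 allows a participant to be classed as lost after 5 silent weeks from discharge, though weekly follow-up runs to 3 months and no check of vital status or readmission is required first

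*Protocol*

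**What the plan says.** Protocol section 6.1 sets the schedule: "After discharge, follow-up information is obtained on a weekly basis until 3 months post-treatment". The period is described as a "follow-up period of 3 months starting post-treatment on Day 0". The next sentence after the weekly schedule is the loss rule: "When no response is received within 5 weeks following discharge the participant may be considered as lost to follow-up". No condition is attached to it.

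Two kinds of outcome depend on contact after discharge:

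- **Safety.** Section 5.4 defines the safety outcome as "measuring the incidence of adverse events up to 3 months post-treatment".
- **Mortality.** Section 5.3 lists "All-cause mortality (time from randomization to death within 4 weeks") among the other outcomes of interest.

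Section 9.1.4.1 makes a general commitment: "Every effort will be made to contact the trial subject and obtain complete data for follow-up". It also names medical charts, discharge summaries and the general practitioner as further sources, to be used where necessary. Section 9.2.1 repeats these sources under Visit 7. Section 6.1 does not refer to either place.

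A missing-data method is given for the primary variable only (Protocol 11.5, SAP 14.9). Neither document says how a lost patient enters the 4-week mortality or 3-month safety summaries.

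**The concern.** The loss rule is shorter than the follow-up it serves. Five weeks would suit a 4-week follow-up, and traces of one remain. Protocol 8.2.1 places the telephone interviews four weeks after the last dose, and 9.1.5 refers to a final 4-week visit. SAP section 4 gives a four-week safety follow-up, and SAP section 3 and Table 1 attach Week 4 to Visit 7. These traces suggest that the rule was not revised when follow-up was extended. That is an inference; neither document says so.

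Silence may also carry information. A patient who has died or been readmitted may be unable to take the call. If such patients can be closed without anyone looking at a record, the events most relevant to safety are the ones most easily missed. The trial is open-label and multi-center, and the wording leaves closure to discretion, so practice could differ between sites.

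**Working it through.** The check is calendar arithmetic.

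**Inputs**
- Loss rule: 5 weeks = 35 days from discharge (6.1).
- Follow-up: 3 months from Day 0 (6.1), taken as 13 weeks = 91 days.
- Discharge: Day 4 is used as an early case, because eligibility requires an expected stay of four calendar days (7.1). Later days up to Day 28 are assumed for range.

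**The plan's own figure.** Section 6.1 says that "participation will be approximately 14 weeks (+/- 5 days"), which is 98 ± 5, or 93 to 103 days. It also says: "Screening phase duration is up to 48 hours".
- Screening plus 3 months from Day 0: 2 + 91 = 93 days, inside the range.
- Screening plus 3 months from the last dosing day (Day 3): 2 + 3 + 91 = 96 days, inside the range.
- Three months added after the 14-day intervention period: 14 + 91 = 105 days, or 107 with screening, outside the range.

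The stated duration therefore agrees with a follow-up that ends at about Day 91 to 94.

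**When the label can apply, and what is left**
- Label day = discharge day + 35.
- Days left = 91 − label day.
- Share = days left / (91 − discharge day).
- Calls left = whole weeks from discharge to Day 91, minus 5.

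| Discharge | Label from | Days after Day 28 | Days left to Day 91 | Share of post-discharge schedule | Weekly calls left |
|---|---|---|---|---|---|
| Day 4 | Day 39 | 11 | 52 | 52/87 = 60% | 7 |
| Day 7 | Day 42 | 14 | 49 | 49/84 = 58% | 7 |
| Day 14 | Day 49 | 21 | 42 | 42/77 = 55% | 6 |
| Day 28 | Day 63 | 35 | 28 | 28/63 = 44% | 4 |

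If the 3 months run from Day 3, the end is Day 94 and 31 to 55 days are left. The label never precedes Day 28: even discharge on Day 0 would give Day 35.

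**Outer bound on a 3-month comparison (loss rates assumed).** Suppose 5%, 10% or 15% of each arm had unknown status: 4 + 2, 8 + 4 or 12 + 6 of 80 + 40. Compare counting all of them as event-free with counting every lost patient in one arm, and none in the other, as having the event. The risk difference moves by up to 5, 10 or 15 percentage points either way (4/80 = 2/40 = 5%, and so on). This is a limit, not an estimate.

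**The case against.** The strongest reply is that the protocol already provides for these patients. Section 9.1.4.1 promises every effort, includes death within 4 weeks in what is assessed, and supplies charts, discharge summaries and the general practitioner. Five weeks of silence is an obvious occasion to use them. The rule is also permissive, nothing says that calls must stop, and it covers only patients with no response in the 5 weeks after discharge. The primary endpoint is at Day 7, the endpoints in the ordered testing sequence end by Day 14, and safety is not formally tested.

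Most of this stands, and it limits the severity. It does not remove the gap, because a site can follow 6.1 to the letter and close a patient without opening a chart.

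Three stronger readings are tempting, and the documents do not support them:

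- **That the rule loses Day-28 outcomes, and so understates 4-week mortality.** The label comes on Day 39 at the earliest for a Day-4 discharge. A patient silent since discharge has the same unknown Day-28 status with or without it. What is lost is the later opportunity to establish a dated death from records.
- **That lost patients are censored at discharge.** No censoring date is given anywhere. The Synopsis names Kaplan-Meier plots for death without one, and nothing says that a death found in a chart would be ignored.
- **That a number of missed deaths, or an imbalance between arms, can be stated.** The documents give neither the unreachable share nor its mortality. The drop-out allowance of about 10% is stated for the Day-7 endpoint and cannot be carried over. Any count would also have to assume that the record sources find nothing.

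**Conclusion.** The inconsistency is real and limited. Section 6.1 permits closure 28 to 52 days before its own follow-up ends, with about 4 to 7 weekly calls unmade. It does so without requiring sources that the protocol names elsewhere. The outcome chiefly exposed is 3-month adverse-event incidence, including late deaths and readmissions. For 4-week mortality, the cost is the forgone retrospective check.

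The ranges assume that 3 months is 91 days from Day 0 and that discharge falls on Days 4 to 28. Severity is minor to moderate: mortality is an other outcome, analysed descriptively and exploratorily, and safety is summarized without formal tests. The number of days alive (5.2) has no stated horizon and would also be touched if it were counted to 3 months. The change is worth making because the present sentence cuts across the plan's own schedule and the remedy is cheap.

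**What to change.** Replace the loss sentence in section 6.1 with wording to this effect:

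*Weekly contact attempts continue until 3 months post-treatment. A participant who has not withdrawn consent is classed as lost to follow-up only at the end of that period. Before that, documented checks of medical charts, discharge summaries and the general practitioner (section 9.1.4.1) must have failed to establish vital status and readmission at Day 28 and at 3 months.*

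Add a line to the SAP: any death or SAE date found by this route is used in the 4-week mortality and 3-month safety summaries, and the number with unknown status at each time is reported by arm.

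A smaller change would keep the 5-week label but require the documented checks first. That would recover earlier events, but it could still miss events between closure and Day 91.

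The cost is one amended protocol sentence, one SAP line, and about 4 to 7 further call attempts plus one record check per unreachable patient. All the sources are already in the protocol.
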